#### **4.3.2 Assessment of Bupivacaine Toxicity and Removal of Implants Due to Bupivacaine Systemic Toxicity**

Patients in this study will be domiciled in a monitored setting at least through 72 hours posttreatment. In addition to the general adverse event monitoring in this setting, patients will be specifically queried and assessed for signs and symptoms potentially indicative of systemic bupivacaine toxicity at multiple time points during the study using the following list of signs and symptoms:

- respiratory difficulty
- change in level of consciousness
- restlessness
- anxiety
- difficulty speaking or being understood
- lightheadedness
- numbness and tingling of the mouth and lips
- metallic taste
- tinnitus (ringing in ears)
- dizziness
- changes in vision
- tremors
- depression
- drowsiness

Assessment of patients for signs and symptoms potentially indicative of systemic bupivacaine toxicity will be made after Time 0/implantation at the following time points: 0.5, 1, 2, 3, and 4 hours (each  $\pm 15$  minutes); 5, 7, 9, 12, 15, 18, 24, 48, and 72 hours (each  $\pm 1$  hour); and on days 7 and 15.

Innocoll

Clinical Study Protocol With Amendment 02

Study INN-CB-024

Controlled Study-Postsurgical Analgesia

If any of these signs or symptoms are assessed (and recorded) as an adverse event(s), the severity of the adverse event(s) will be scored based on the adverse event grading scale of the Common Terminology Criteria for Adverse Events (CTCAE) version 5.0 as follows:

Grade	Description
1	Mild ; asymptomatic or mild symptoms; clinical or diagnostic observations only; intervention not indicated
2	Moderate ; minimal, local, or noninvasive intervention indicated; limiting age-appropriate instrumental activities of daily living
3	Severe or medically significant but not immediately life-threatening; hospitalization or prolongation of hospitalization indicated; disabling; limiting self care activities of daily living
4	Life-threatening consequences ; urgent intervention indicated
5	Death related to adverse event

If a patient experiences a grade 4 adverse event of any of the following:

- respiratory difficulty
- change in level of consciousness
- cardiovascular event
- 3 or more of the other signs and symptoms on the list concurrently

bupivacaine plasma concentrations will be obtained and the investigator may request that the patient's treatment be unblinded. If the patient received INL-001, the investigator may make the decision to remove the implants as part of the patient's treatment plan for these adverse events. If at all possible, the investigator should discuss the case with the medical monitor before proceeding.

The decision to return a patient to the operating room in order to remove INL-001 implants will be an individualized assessment made on the basis of multiple patient factors (eg, age, comorbidities, hemodynamic status). The determination regarding returning a patient to the operating room for removal of INL-001 implants will be made by the investigator.

#### 4.4 Replacement of Patients

There is no provision for replacing patients.

#### 4.5 Rescreening

A patient who is screened but not enrolled, such as because inclusion/exclusion criteria were not met or enrollment did not occur within the specified time, may be considered for screening again if, for example, there is a change in the patient's medical background or a modification of study inclusion and exclusion criteria.

Patients may have individual parameters retested at the discretion of both the investigator and the sponsor.

If the patient is rescreened, another ICF must be signed.

Innocoll

Clinical Study Protocol With Amendment 02

Study INN-CB-024

Controlled Study-Postsurgical Analgesia

---

#### **4.6 Screening Failure**

Screening failures are defined as potential participants who consent to participate in the study but are not subsequently enrolled in the study. Minimal information to be recorded includes demography and screening failure details, including eligibility criteria.

Innocoll

Clinical Study Protocol With Amendment 02

Study INN-CB-024

Controlled Study-Postsurgical Analgesia

## **5 TREATMENT**

Additional information about study drug handling, administration, accountability, and disposition may be found in the study pharmacy manual.

### **5.1 Investigational Medicinal Product Used in the Study and Other Treatment Information**

The test study drug used in this study is the INL-001 [XARACOLL® (bupivacaine hydrochloride) implant] (batch/lot 2000231; expiry September 2022; manufacturer Syntacoll GmbH, [name]).

The comparison study drug used in this study is the placebo (drug-free/collagen) implant (batch/lot 20000210; expiry September 2022; manufacturer Syntacoll GmbH, [name]).

INL-001 is a drug-device combination product containing 100 mg of bupivacaine HCl per implant, equivalent to 88.8 mg of bupivacaine, for placement in the surgical site. The dose to be evaluated is three 100-mg implants (300 mg bupivacaine HCl), equivalent to 266.4 mg of bupivacaine. Each implant is 5 cm × 5 cm × 0.5 cm in size and is white to off-white in color. Placebo implants contain collagen but no bupivacaine. Implants are terminally sterilized.

Additional details may be found in the IB for INL-001.

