### CLINICAL STUDY PROTOCOL SYNOPSIS

#### Study INN-CB-024

**Title of Study:** A Randomized, Double-blind, Placebo-controlled Study to Evaluate the Efficacy and Safety of a 300-mg Dose of the INL-001 (Bupivacaine Hydrochloride) Implant in Patients Undergoing Abdominoplasty

**Sponsor:** Innocoll Pharmaceuticals Limited

**Investigational New Drug (IND) Number:** 77,127

**New Drug Application (NDA) Number:** 209511

**Test Investigational Medicinal Product (Study Drug) Dose, Pharmaceutical Form, Route of Administration, and Administration Rate:** The test study drug used in this study is the INL-001 [XARACOLL® (bupivacaine hydrochloride) implant] (batch/lot 20002310; expiry September 2022; manufacturer Syntacoll GmbH, [name]).

INL-001 contains 300 mg of bupivacaine hydrochloride (HCl) (three 100-mg implants), equivalent to 266.4 mg of bupivacaine, and is implanted in a single administration.

**Comparison/Reference Investigational Medicinal Product:** The comparison study drug used in this study is the placebo (drug-free/collagen) implant (batch/lot 20000210; expiry September 2022; manufacturer Syntacoll GmbH, [name]).

**Type of Study (Phase):** Efficacy and safety (Phase 3)

**Indication:** Placement in the surgical site to produce postsurgical analgesia following abdominoplasty

**Number of Investigational Centers Planned:** Up to 8

**Countries Planned:** United States (US)

**Planned Study Period:** The study is expected to start at a time to be determined, with an estimated enrollment period of approximately 6 months, including an interim analysis. Screening to the end of the study for each patient will be a maximum of 75 ( $\pm 3$ ) days.

**Planned Number of Patients:** Up to approximately 432 patients will be screened in order to randomize 372 patients to achieve a minimum of 360 patients randomized and treated [180 evaluable patients per treatment group]).

**Study Population:** Men and women 18-65 years of age

**Primary Objective:** The primary objective of the study is to evaluate the analgesic effect of treatment (ie, efficacy) with INL-001 implants compared with placebo implants after placement into the surgical site during abdominoplasty.

**Secondary Objectives:** The secondary objective is to assess the safety and tolerability of INL-001 implants after placement in the surgical site during abdominoplasty.

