### **5.2.3 Accountability**

The investigator will ensure that adequate records showing the receipt, dispensing, return, or other disposition of the study drug, including the date, quantity, batch or code number, and identification of study patients (number and initials) who receive the study drug are maintained. The investigator will not supply the study drug to any person except subinvestigators (as submitted to the local regulatory authority), designated staff, and patients in this study. The investigator will not dispense the study drug from any sites other than those submitted to the local regulatory authority. The study drug will not be relabeled or reassigned for use by other patients.

Innocoll

Clinical Study Protocol With Amendment 02

Study INN-CB-024

Controlled Study-Postsurgical Analgesia

Each study drug shipment will include a packing slip listing the contents of the shipment, return instructions, and any applicable forms.

The investigator is responsible for ensuring deliveries of the study drug and other study materials from the sponsor are correctly received, recorded, handled, and stored safely and properly in accordance with the Code of Federal Regulation (CFR) or national and local regulations, and used in accordance with this protocol.

Only patients enrolled in the study may receive the study drug and only authorized staff at the investigational center may supply or administer the study drug, which must be stored in a secure, environmentally controlled, and monitored (manual or automated) area in accordance with the labeled storage conditions or appropriate instructions with access limited to the investigator and authorized staff at the investigational center.

The investigator, institution, or head of the medical institution (where applicable) is responsible for study drug accountability, reconciliation, and record maintenance (ie, receipt, reconciliation, and final disposition records).

A record of study drug accountability (ie, study drug and other study materials received, used, retained, returned, or destroyed) must be prepared and signed by the principal investigator or designee with an account given for any discrepancies. Upon completion of the study, unused study drug will be returned to the sponsor's designee.

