### **5.10 Randomization and Blinding**

Eligible patients will be randomly assigned to treatment in a 1:1 ratio to receive either INL-001 or placebo collagen implants. Patients will not be aware of their treatment allocation and all study staff involved in efficacy and safety assessments will be blinded to treatment assignments until after database lock and release of unblinding randomization codes. Emergency unblinding is allowable if deemed necessary by the investigator, and discussed and agreed with the study medical monitor, for the safety of the patient and will be fully documented and included in protocol deviations. Patients will be stratified by study center and body mass index (BMI) ( $<30 \text{ kg/m}^2$  and  $\geq 30 \text{ kg/m}^2$ ). In the case of a suspected unexpected serious adverse reaction (SUSAR), unblinding of the sponsor will be performed according to the safety management plan.

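### The protocol held by blinded investigators prints arm-specific lot numbers, and section 5.2.3 lets site records tie a batch number to a patient: an avoidable route to unblinding

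*Protocol*

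**What the plan says.** The synopsis identifies the INL-001 supply as "batch/lot 20002310; expiry September 2022". Section 5.1 identifies it as "batch/lot 2000231; expiry September 2022". For placebo, section 5.1 has "The comparison study drug used in this study is the placebo (drug-free/collagen) implant (batch/lot 20000210; expiry September 2022", and the synopsis agrees with it. The summary of changes for Amendment 01 records that lot details were added to the treatment section at that point.

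Section 5.2.3 makes the investigator answerable for records of receipt, dispensing and return, "including the date, quantity, batch or code number, and identification of study patients (number and initials) who receive the study drug are maintained". It adds that the accountability record "must be prepared and signed by the principal investigator or designee".

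Section 5.10 requires that "all study staff involved in efficacy and safety assessments will be blinded to treatment assignments until after database lock and release of unblinding randomization codes".

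**The concern.** A lot number is harmless while nobody outside supply can link it to an arm. Here the protocol supplies that link to the people who are meant not to have it, and section 5.2.3 permits the record that would make use of it. Reading the two together takes no unblinding request. Emergency unblinding under section 5.10 needs the medical monitor's agreement and documentation; a glance from a log to section 5.1 would bypass that control and leave no trace.

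Several outcomes depend on staff who do not know the allocation. The investigator or subinvestigator assesses toxicity signs, wound healing and wound grade (sections 7.1.6.1 to 7.1.6.3), and the investigator judges causality (section 7.1.4). Rescue is also partly in staff hands, because patients with low pain scores are discouraged from taking opioids and the investigator judges whether pain is unrelieved before intravenous morphine is given (sections 3.1 and 5.4). That bears on the opioid-free key secondary endpoints. If unblinding did occur this way, the analysis could neither detect it nor correct for it.

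**Working it through.** No sample size, power or error rate is involved, so the check is a comparison of the text.

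**1. The lot numbers.**

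| Arm | Synopsis | Section 5.1 |
|---|---|---|
| INL-001 | 20002310 | 2000231 |
| Placebo | 20000210 | 20000210 |

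One lot is listed per arm. The two INL-001 entries differ by a final digit, so at least one is wrong. Both differ from 20000210, so the arms can be told apart whichever is correct.

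**2. Who holds the list.** Section 10.1 has investigators sign protocol amendments. The lot numbers sit in the body and synopsis of the amended protocol, so blinded investigators have them.

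**3. Whether a site record may contain the lot.** Section 5.2.3 offers two alternatives, a batch number or a code number, recorded with patient number and initials. The lot is therefore permitted but not required. Section 13.4.2 has the investigator retain the reports of receipt, use and disposition.

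**4. Whether the lot is on the kit or packing slip.** Section 5.2.2 lists label items, including a description of the contents and an open-ended allowance for other required items. The lot is neither named nor excluded. Section 5.2.3 says that a packing slip lists the shipment's contents and does not mention lots. Section 3.5.2.1 assigns treatment by kit number.

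**5. Whether the person responsible for the record must be blinded.** The investigator is an assessor under sections 7.1.4 and 7.1.6, and so falls within section 5.10. Section 5.2.3 allows a designee to prepare and sign the accountability record, but it does not require that person to be separate from assessment. The protocol describes no unblinded pharmacist, no masked or common lot, and no rule keeping lot numbers from blinded staff.

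**6. What a visible lot would reveal.** Under 1:1 allocation, a guess at the arm is right with probability 1/(1+1) = 50%. If a true listed lot is seen, the probability becomes 100% for that patient. If it is not seen, it stays at 50%.

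Steps 1 to 3 are established by the text. Step 4 leaves open whether the lot is ever visible, and step 6 depends on it.

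**The case against.** The strongest reply is that the essential link is missing. Two lot numbers in a protocol reveal nothing unless site staff also see the lot of a particular kit, and no section says that they do. A site that records only the kit code complies fully with section 5.2.3. The label section does not call for a lot number, the listed expiry is the same in both arms, and nothing says that the description of contents differs. Section 5 refers to a study pharmacy manual for handling and accountability; masked lots or an unblinded pharmacist could well be set out there. All of this stands, and it limits the point to an open route.

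Three stronger readings are tempting, and the documents do not support them:

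- **Sections 5.2.3 and 5.10 contradict each other.** They do not. A code number, or a designee outside the assessment team, satisfies both.
- **Allocation concealment before assignment is lost.** That would require lot numbers to be visible on stored kits, which the protocol does not state.
- **The false-positive rate rises by a stated amount.** Any such figure needs an assumed bias, and the protocol offers no basis for one. SPI24 is built from patients' own pain scores, and patients are blinded too, so staff knowledge could affect it only indirectly.

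It is also fair to say that section 5.1 does not rule out further lots, particularly as up to 180 patients may be added after the interim analysis. An unlisted lot would not be decoded by the list; a listed one still would be.

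What the reply does not answer is why the protocol prints the key at all. Blinded sites do not need it, and a safeguard in another document would not remove it from this one.

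**Conclusion.** The point holds as an avoidable weakness in how blinding is protected. The protocol publishes a lot-to-arm key to investigators who must be blinded, and it permits the site record that would use the key. Section 5.10 is left unprotected by the protocol text; it is not shown to be breached.

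The size is conditional. Where the true lot is visible or recorded, the arm is identified with certainty; where it is not, nothing is revealed. The documents do not say how many of the 360 planned treated patients would be in either position, and no effect on the endpoints can be calculated. The conclusion assumes that the lots listed are those supplied and that each lot serves one arm, as section 5.1 presents them. The unseen pharmacy manual may already restrict what sites see, which would reduce the practical risk.

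The mismatch in the INL-001 lot number is a separate and certain error that needs reconciling in any case. This is a cheap improvement worth making at the next amendment, not a fault that calls the design into question.

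**What to change.** - **Synopsis and section 5.1:** remove the arm-specific lot numbers. Hold them in a restricted document kept by unblinded supply staff, and report them in the clinical study report. Reconcile 20002310 with 2000231 against supply records when doing so.
- **Section 5.2.3:** replace the choice between a batch and a code number with the blinded kit number only.
- **Sections 5.2.2 and 5.2.3:** state that labels, packing slips and site logs carry only the kit number or one common packaging lot, with identical contents wording in both arms. If the pharmacy manual already says this, a cross-reference is enough.

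The cost is a wording change and a check of kits and packing slips, with over-labelling if a true lot is found on them. No patients, visits or analyses are added. The downside is that lot traceability, for example in a recall, moves from the site log to the unblinded supply list, which must link kit number to lot and be reachable when needed.

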#### **5.1.1 Anesthetic Protocol**

The standardized anesthetic regimen will include general anesthesia with fentanyl (maximum dose of 4 mcg/kg) and propofol (dose at discretion of the anesthesia provider), with or without volatile anesthetics or muscle relaxants. The standardized anesthetic regimen is a guide that should be followed to minimize interpatient variability to the greatest extent possible. However, it is understood that hemodynamic fluctuations and other intraoperative events may necessitate some deviation from this standard regimen. Neuraxial techniques, such as epidural and spinal anesthesia, are not allowed. No epinephrine is permitted during the procedure. No local anesthetic other than INL-001 (study drug) in the surgical field or regional anesthesia is permitted. Lidocaine HCl 1% injection at a dose of no more than 20 mg may be administered once through iv access to decrease venous irritation (eg, as caused by propofol) at the time of surgical anesthesia. Intraoperatively, fentanyl (maximum dose of 4 mcg/kg) is permitted for analgesia. No other analgesic agents may be used during the procedure including, but not limited to, opioids (other than fentanyl), acetaminophen (oral or iv), NSAIDs (eg, ketorolac or COX-2 inhibitors), ketamine, pregabalin, and others. A preoperative dose of an antiemetic, ondansetron iv 4 mg, for nausea prophylaxis is allowed; however, postoperative antiemetic medications should be given to treat only patients who report nausea and/or vomiting. Administration of fentanyl should be avoided 30 minutes prior to the anticipated conclusion of the procedure if medically acceptable in the judgement of the anesthesiologist.

Innocoll

Clinical Study Protocol With Amendment 02

Study INN-CB-024

Controlled Study-Postsurgical Analgesia

### **5.1.2 Placement of Study Drug**

Following tissue removal and repair of the abdominal musculature, 2 implants should be placed on the rectus diastasis at the site of rectus sheath plication and 1 implant should be placed below the abdominal incision between Scarpa's fascia and the subcutaneous fat. The implants should, to the greatest extent possible, be placed so they span the fascia that is exposed prior to surgical closure. Implants may be divided to accommodate placement, but an individual implant may not be cut into more than 2 halves.

## **5.2 Preparation, Handling, Labeling, Storage, and Accountability for the Study Drug**

### **5.2.1 Storage and Security**

The investigator or designee must record that appropriate temperature conditions have been maintained for the study drug received and that any discrepancies are reported and resolved before use of the study drug.

Study drug must be stored at 20°C to 25°C (68°F to 77°F) with excursions permitted between 15°C and 30°C (between 59°F and 86°F). Brief exposure to temperatures up to 40°C (104°F) may be tolerated provided the mean kinetic temperature does not exceed 25°C (77°F) (United States Pharmacopeia [USP] Controlled Room Temperature); however, such exposure should be minimized.

To prevent theft or diversion, study drug must be stored securely locked in an appropriate enclosure. Any actual or suspected theft or diversion must be reported to the sponsor immediately.

### **5.2.2 Clinical Supply Label**

The study drug will be labeled with the sponsor's name and address, description of contents, storage conditions, and any other applicable item required by national and regional guidelines/regulations. The label will contain the statement "Investigational Product: To be used in a clinical investigation only" or other similar/appropriate statement.

Supplies of study drug will be labeled according to the current International Council for Harmonisation (ICH) guidelines on Good Clinical Practice (GCP) and Good Manufacturing Practice (GMP) and will include any locally required statements.

### **5.2.3 Accountability**

The investigator will ensure that adequate records showing the receipt, dispensing, return, or other disposition of the study drug, including the date, quantity, batch or code number, and identification of study patients (number and initials) who receive the study drug are maintained. The investigator will not supply the study drug to any person except subinvestigators (as submitted to the local regulatory authority), designated staff, and patients in this study. The investigator will not dispense the study drug from any sites other than those submitted to the local regulatory authority. The study drug will not be relabeled or reassigned for use by other patients.

Innocoll

Clinical Study Protocol With Amendment 02

Study INN-CB-024

Controlled Study-Postsurgical Analgesia

Each study drug shipment will include a packing slip listing the contents of the shipment, return instructions, and any applicable forms.

The investigator is responsible for ensuring deliveries of the study drug and other study materials from the sponsor are correctly received, recorded, handled, and stored safely and properly in accordance with the Code of Federal Regulation (CFR) or national and local regulations, and used in accordance with this protocol.

Only patients enrolled in the study may receive the study drug and only authorized staff at the investigational center may supply or administer the study drug, which must be stored in a secure, environmentally controlled, and monitored (manual or automated) area in accordance with the labeled storage conditions or appropriate instructions with access limited to the investigator and authorized staff at the investigational center.

The investigator, institution, or head of the medical institution (where applicable) is responsible for study drug accountability, reconciliation, and record maintenance (ie, receipt, reconciliation, and final disposition records).

A record of study drug accountability (ie, study drug and other study materials received, used, retained, returned, or destroyed) must be prepared and signed by the principal investigator or designee with an account given for any discrepancies. Upon completion of the study, unused study drug will be returned to the sponsor's designee.

